3.1. Primary Endpoint

The primary co-endpoints are the BRIEF2/P Global Composite Score and the GNG signal detection parameter (d').

3.2. Secondary Endpoints

Secondary measures include data from the following domains:

- Objective performance testing
 - Vigilance/attentional skills: Go-No-Go test subtests
 - Fine motor coordination: NIH-Toolbox 9-Hole Pegboard Dexterity Test
- Behavioral scales (note that several measures utilize a date stamp when questionnaires are entered electronically into the commercial scoring websites)

- Executive function: BRIEF2/P meta-cognition and emotional regulation summary scores and subscales for parent and teacher reports; BRIEF2/P teacher report global composite score and subscores
 - Behavior: Child Behavior Checklist (CBCL) summary scale and subscores, parent and teacher responses
 - Attention: Conners 3 Short Form (caregiver and teacher versions) Global Index T score and subscales
 - Adaptive Behavior Measure System, 3rd Edition (ABAS-III), a measure of children's everyday functioning (this measure is centrally scored, and date of birth as well as date of study and study ID is required to be entered into the WPSpublish website)
- SDB symptoms
 - Pediatric Sleep Disordered Breathing Questionnaire (SRBD) total score
 - Sleepiness: Epworth Sleepiness Scale modified for children summary score and SRBD sleepiness scale
 - Snoring: The Tascam DLR-10L Microphone results as an exploratory aim
- Quality of Life
 - Generic: Pediatric Quality of Life Inventory (PedsQL) total score and subscores
 - Disease specific: OSAS-18 total score
- Physical exam
 - Measurements of weight; height; body mass index (BMI); waist, hip, neck circumferences
 - Systolic, diastolic, and mean blood pressure levels
- Health Care Utilization
 - Medications, health care visits (scheduled, unscheduled), ascertained from caregiver reports, EMR surveillance, billing and pharmacy records, hospitalizations.

3.3. Sample Descriptors and Potential Effect Modifiers

- Demographics: race, SES (parent education, family income, financial stress rating scale, geocode data on neighborhood characteristics)
- Asthma/atopy: IgE, International Study Of Asthma And Allergies In Childhood (ISAAC) questionnaire, review of EMR and parent interview (using NHLBI asthma definitions based on a history of asthma and use of asthma medications)
- Second-hand smoke exposure: urinary cotinine
- Family functioning cluster: family functioning (Family Assessment Device, short form); parenting style (Parenting Style Questionnaire); parent perception of stress (Parenting Stress Index 4th Ed., short form); medical literacy (Rapid

Estimate of Adult Literacy in Medicine, Revised); discrimination (Experiences of Discrimination)

- COVID-19 Survey

4. Participant Criteria

4.1. Study Population

This study will involve participation of children with symptoms of MSDB and their caregivers. Both genders and all racial and ethnic groups will be eligible for participation. Dyads (child and one caregiver) will be included. The following inclusion and exclusion criteria refer to the child participant only. There are no specific inclusion/exclusion criteria for the caregiver participant. The caregiver participant will be the parent/guardian providing informed consent or accompanying the child on the study visits.

4.2. Inclusion Criteria

1. Ages 3.0 to 12.9 years at the time of screening
2. Diagnosed with MSDB defined as:
 - a. Parent report of habitual snoring that occurs most of the night on at least 3 nights per week, and has been present for at least 3 months (on average occurring > 3 nights per week or more than one-half the sleep time) *and*
 - b. Obstructive apnea index < 1/hr or obstructive apnea hypopnea index < 3 /hr and no desaturation < 90% in conjunction with obstructive events, confirmed on nocturnal, laboratory-based PSG

NOTE: Participants failing baseline screening PSG will be referred for clinical care.

3. Tonsillar hypertrophy ≥ 2 based on a standardized scale of 0-5
 - a. 0 = surgically absent
 - b. 1 = taking up < 25% of the space between the tonsillar pillars
 - c. 2 = taking up 25-50% of the space between the tonsillar pillars
 - d. 3 = taking up 51-75% of the space between the tonsillar pillars
 - e. 4 = taking up > 75% of the space between the tonsillar pillars
4. Deemed to be a candidate for AT by ENT evaluation, i.e., no technical issues that would be a contraindication for surgery such as submucous cleft palate.
5. Primary indication for AT is nocturnal obstructive symptoms (i.e., not recurrent infections or other indications)

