Short Title	PATS (Pediatric Adenotonsillectomy for Snoring)
Special Population	Children (male and female), ages 3.0 to 12.9 years of age
Methodology	Parallel, randomized, single blind, multi-center design
Study Duration	5 years
Clinical Study Center(s)	Multicenter (7)
Objectives	
1. Determine the effect of early adenotonsillectomy (eAT) on behavior (primary outcome), sleep-disordered breathing (SDB) symptoms, and quality of life.
 
2. Determine the effect of AT on health care utilization (HCU) in children with MSDB.
 
3. Identify factors that moderate the response to surgery: age, socioeconomic status, asthma and atopy, second hand tobacco smoke exposure, family functioning, short sleep duration, obesity, minority status

Number of Participants	460
Diagnosis and Main Inclusion Criteria	Diagnosis of mild sleep-disordered breathing (MSDB) defined by an obstructive apnea index (OAI) <1/hr or an apnea hypopnea index (AHI) <or =3.0 /hr confirmed by nocturnal polysomnography (PSG); parental report of habitual snoring (on average occurring > 3 nights per week); tonsillar hypertrophy $\geq 2 +$; deemed to be a surgical candidate for adenotonsillectomy (AT) by ENT evaluation
Study Intervention	Early Adenotonsillectomy (eAT)
Reference Intervention	Watchful Waiting with Supportive Care (WWSC)
Duration of Follow-Up	12 months
Statistical Methodology	Primary analyses will follow the "intention-to-treat" principle; that is, individuals will be analyzed according to their assigned treatment group, whether or not they remain on the study treatment. The co-primary outcomes will be the change in executive behavior relating to self-regulation and organizational skills (as measured by the Behavior Rating Inventory of Executive Function [BRIEF2/P] Global Composite Score) and vigilance (as measured on the Go-No-Go [GNG]) between the eAT and WWSC groups at 12 months. Analyses addressing secondary aims will be considered exploratory. Details of the statistical plan are outlined in the Data Coordinating Center application.

Rationale for the PATS Study

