Participants will undergo a standardized assessment of behavior, behavioral performance testing, and other health-related evaluations at baseline and 12 month follow-up time points. At 6 months caregivers will complete neurobehavioral assessments remotely. Virginia will have a 6 month visit in person and repeat baseline assessments. Participants will receive monthly check-in by telephone, , email and/or text messaging in order to maximize retention and to collect additional symptom and HCU reports. Text messaging will only be utilized with families who agree to receive text messages. After 12 months, children who did not get surgery who have a 12-month

PSG showing obstructive sleep apnea (apnea hypopnea index ≥ 3 /hr or obstructive index > 1 /hr) or whose parent reports ongoing symptoms/concerns will be referred back to ENT for further clinical management (such as adenotonsillectomy) as per standard clinical care.

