2.4.3. Follow-up Contacts

eAT arm only: AT surgery 1-4 weeks from randomization within Month 1

WWS arm only: ENT re-evaluation visit with 1-4 weeks after Endpoint Visit if indicated by 12-month PSG revealing obstructive sleep apnea (AHI ≥ 3.0 /hr. or obstructive apnea index > 1 /hr.) or parent reporting concerning symptoms.

Both groups:

- Monthly contact by telephone, email and/or text messaging , for health care utilization, medication, adverse event inquiries and to support study participation.
- Check In questionnaires and surveys will be completed bi-monthly, at months 2, 4, 6, 8, and 10.
- Interim remote visit at 6 months for caregiver questionnaires and neuro behavioral assessments, adverse event and health care utilization inquiry, and teacher forms of behavior rating scales.
 - Virginia will have in person child neurobehavior testing in addition to assessments above.
- Endpoint Visit at Month 12 for behavioral and performance testing; questionnaires; anthropometry, and BP measures. Behavioral rating scales mailed to teachers.
- Follow-up research PSG at Month 12
- Follow up questionnaires after participation ended to assess feasibility of conducting a study to evaluate long-term outcomes of mild SDB

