4. The centrally scored PSG report will be transmitted from the DCC/Reading Center to the clinical site where it will be imported into a study eligibility file. Based on the PSG findings, ENT evaluation and initial eligibility criteria, preliminary eligibility will be determined. Families will be contacted, consent will be re-affirmed, and the baseline visit will be scheduled. *Note:* Children with PSG results that exceed the AHI or desaturation criteria after central review are ineligible for participation regardless of the local clinical interpretation of the PSG data.
5. Baseline and follow up visits will aim to collect data representative of the child's usual health status. Thus, PSG, baseline and follow up visits will not occur earlier than 30 days from the time of an acute exacerbation of illness requiring hospitalization, or oral steroid medication "burst". When a child has other symptoms such as a fever or nasal/respiratory illness, then the baseline and follow-up visits/exams *excluding PSG* (see stipulations above) will not be scheduled or occur within 14 days from the time of a febrile illness.

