8.2. Participants Randomized to Watchful Waiting with Supportive Care

After 12 months, children who did not get surgery who have a 12-month PSG showing obstructive sleep apnea (apnea hypopnea index >or =3.0 /hr or obstructive index > 1/hr) or whose parent reports ongoing symptoms/concerns will be referred back to ENT for further clinical management (such as adenotonsillectomy) as per standard clinical care.

9. Study Procedures

A study visit schedule is provided in Appendix A. Visit time points, study procedures and assessments are listed in the order in which they occur.

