9.1.2. Screening PSG

All potential participants who meet the initial eligibility criteria will be evaluated through a standardized PSG prior to the baseline exam. PSG results that do not meet AHI/saturation criteria after central review by the Reading Center are ineligible for participation regardless of the local clinical interpretation of the PSG data and the baseline visit will not be scheduled. Baseline PSG data can be obtained in two ways:

1. A proportion of PSGs may have been performed as part of routine clinical care. PSG data (performed for clinical purposes within 60 days prior to the baseline/randomization visit) will be transmitted to the Reading Center where they will be re-scored to ascertain PSG eligibility and entry into the study. If a clinical PSG has been performed more than 60 days prior to baseline/randomization or was not performed using agreed upon research sensors and montages, then a research PSG must be performed.
2. Potential participants who have not undergone a PSG within 60 days prior to the baseline/randomization visit will undergo a research PSG. Resulting PSG data will be transferred to the Reading Center within 48 hours to determine PSG eligibility and to collect research quality data.

9.1.3. 12 Month Endpoint PSG

2 weeks before or 2 weeks after the scheduled Month 12 daytime visit, all participants will undergo a research PSG. Data will be transmitted to the Reading Center and results will be scored (refer to the PSG Manual of Procedures).

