9.7.1. Screening visit/PSG eligibility – Day -60 to -1

At this visit, preliminary study eligibility is confirmed and informed consent obtained. If the participant had a clinical PSG, then these data are sent to the DCC/ Reading Center to confirm eligibility. If the participant has not had a PSG, then a research PSG is performed.

9.7.2. Baseline visit – Day 0

After PSG eligibility for MSDB is confirmed, this visit includes anthropometry, BP measurement and physical examination. The child completes behavioral performance measures and the parent completes questionnaires about behavior & attention, SDB symptoms, sleepiness, quality of life and family functioning. Children \geq 5 years of age also complete the child version of the PedsQL. Urine is collected for cotinine and serum

IgE is collected by venipuncture. The research coordinator inquiries about adverse events, changes in health status or medication, and HCU. Eligibility is confirmed and the participant is randomized. Behavioral rating scales are mailed to teachers.

9.7.3. Monthly Check-In – Months 1, 2, 3, 4, 5, 7, 8, 9, 10, 11

Between each face-to-face visit, study staff will make contact by telephone, email and/or text messaging, with families in both groups for inquiries about adverse events, medications, and changes in health status using a study CRF. HCU is assessed and EMR surveillance completed. Participants are reminded about upcoming study visits and study participation is reinforced.

9.7.4. Remote Interim Visit – Month 6

The parent completes questionnaires about behavior, SDB symptoms, sleepiness, quality of life and family functioning. Study staff inquire about adverse events, changes in health status or medication, and HCU. EMR surveillance is completed. Behavioral rating scales are mailed to teachers. Note that with the Covid-19 pandemic, 6 month visits can be held virtually if in-person visits are not possible, focusing on parent-related questionnaires.

9.7.5. Endpoint PSG – Month 12

Participant completes overnight PSG using the same protocol as for baseline PSG.

9.7.6. Endpoint daytime visit – Month 12

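### Inclusion criterion 2b joins the OAI and AHI limits with *or*, so it admits a PSG that other sections label OSA, a condition the protocol says is excluded; AHI of exactly 3.0 is also classified inconsistently

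*Combined protocol and SAP*

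**What the plan says.** **Entry rule.** Section 4.2, item 2b requires "Obstructive apnea index < 1/hr or obstructive apnea hypopnea index < 3 /hr and no desaturation < 90" per cent during obstructive events. The Study Summary describes the population as "defined by an obstructive apnea index (OAI) <1/hr or an apnea hypopnea index (AHI) <or =3.0 /hr". Both use *or*, but the AHI limit is strict in one and inclusive in the other.

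**Central review.** Section 5.2, item 4: "Children with PSG results that exceed the AHI or desaturation criteria after central review are ineligible for participation". Section 9.1.2: "PSG results that do not meet AHI/saturation criteria after central review by the Reading Center are ineligible for participation". Neither names OAI. Section 5.1 says central scoring confirms the PSG eligibility criteria, which leads back to item 2b. Section 9.7.2 places this before the baseline visit: "After PSG eligibility for MSDB is confirmed, this visit includes anthropometry, BP measurement and physical examination".

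**OSA label at 12 months.** Section 2.1: "PSG showing obstructive sleep apnea (apnea hypopnea index ≥ 3 /hr or obstructive index > 1 /hr". Section 2.4.3: "12-month PSG revealing obstructive sleep apnea (AHI ≥ 3.0 /hr. or obstructive apnea index > 1 /hr". Section 8.2: "PSG showing obstructive sleep apnea (apnea hypopnea index >or =3.0 /hr or obstructive index > 1/hr". Breaching either limit is enough.

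**OSA as an exclusion.** Sections 6.2, 6.6 and 10.4.3 each say that children with OSA do not take part, without giving a number. The exclusion list in section 4.3 has no OSA item.

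**SAP (section 19).** The description of the study says PSG screening is there to remove frank OSA. It repeats the 12-month limits (AHI at or above 3, or OAI above 1) as a referral trigger, without calling them OSA. The Aim 1 secondary analyses say that everyone entered with AHI under 3, treat this as showing no OSA, and define emergent OSA by AHI of 3 or more, with no OAI component.

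**The concern.** The 12-month label makes a PSG OSA if either index is too high. To be free of OSA on that label, a child must be within both limits. The entry rule asks for only one, so it cannot be the complement of the label.

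This criterion defines the trial population. As written, it allows a child whose PSG three sections would call OSA to be randomized, possibly to 12 months of watchful waiting, while three other sections say such children are excluded. The SAP's premise that nobody had OSA at entry then holds only on its own AHI-only definition. If that child's PSG were unchanged at 12 months, section 2.1 would call it OSA and the SAP would count no emergence.

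**Working it through.** There is no plan figure to reproduce. The check codes each rule and applies it to the same PSGs, assuming no desaturation. Indices are per hour.

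**Rules**
- Item 2b: OAI < 1 *or* AHI < 3.
- Study Summary: OAI < 1 *or* AHI ≤ 3.0.
- Central review: the AHI criterion must be met (< 3 from item 2b, or ≤ 3.0 from the Study Summary).
- OSA in sections 2.1, 2.4.3 and 8.2: AHI ≥ 3 *or* OAI > 1. Its negation is AHI < 3 *and* OAI ≤ 1.
- OSA in SAP Aim 1: AHI ≥ 3.

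**Step 1: example PSGs, index names treated as synonyms**

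| OAI, AHI | Item 2b | Study Summary | Central AHI check | OSA by 2.1/2.4.3/8.2 | OSA by SAP |
|---|---|---|---|---|---|
| 0.5, 2.0 | pass | pass | pass | no | no |
| 2.0, 2.5 | pass | pass | pass | **yes** | **no** |
| 0.5, 3.0 | pass (OAI limb) | pass | fail at < 3, pass at ≤ 3.0 | yes | yes |
| 1.5, 3.0 | fail | pass | fail at < 3, pass at ≤ 3.0 | yes | yes |
| 0.5, 10 | pass (OAI limb) | pass (OAI limb) | fail | yes | yes |

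The second row is the main conflict. The third and fourth show the separate problem at AHI 3.0. In the last, central review catches what the literal *or* lets through.

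**Step 2: extent of the conflict.** Take OAI ≤ AHI (assuming obstructive apneas are counted within the AHI), both from 0 to 10 in steps of 0.1: 101 × 102 / 2 = 5,151 pairs. These count rule combinations, not children.
- Pass item 2b but OSA by section 2.1, through the OAI limb (OAI 0.0 to 0.9, AHI 3.0 to 10.0): 10 × 71 = 710.
- The same through the AHI limb (OAI and AHI both 1.1 to 2.9): 19 × 20 / 2 = 190. Total 710 + 190 = 900.
- After the central check at AHI < 3, the 710 go and the 190 remain, that is, 1 < OAI ≤ AHI < 3.
- With *and* in item 2b: 0 remain.
- With the Study Summary limit (≤ 3.0) in both the entry rule and the central check: 31 further pairs at AHI 3.0 remain under *or* (OAI 0.0 to 3.0). Under *and*, 10 remain (OAI 0.0 to 0.9, AHI 3.0).

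**Step 3: index names.** Item 2b says obstructive AHI; the Study Summary, section 2.1 and the SAP say AHI. Section 2.4.3 and the SAP referral trigger say obstructive apnea index; sections 2.1 and 8.2 say obstructive index. If obstructive AHI and AHI differ, a child with OAI 0.5, obstructive AHI 2.5 and AHI 3.5 meets both limbs of item 2b, is OSA by section 2.1, and does not fit the SAP's statement on entry AHI. The result at central review depends on which index is meant. Changing the connector does not close this.

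**Step 4: smaller gaps.** OAI of exactly 1.0 misses the OAI entry limit (< 1) but is not above 1. It is unclear whether the desaturation clause in item 2b attaches to both limbs or only the second, although sections 5.2 and 9.1.2 apply desaturation regardless.

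**The case against.** The either-index OSA label is written for the 12-month PSG and decides who is referred back to ENT. No section gives a numeric definition of OSA at entry. The only text linking an entry number to absence of OSA is in SAP Aim 1, which uses AHI alone, as the central-review wording does. On that reading the exclusion statements, central review and the SAP agree, and OAI 2.0 with AHI 2.5 is a proper entry. Sections 5.2 and 9.1.2 say when a child is out; they do not say nothing else is checked. Eligibility is checked again at the baseline visit and electronically before assignment (sections 9.7.2 and 9.3), and a site could rely on section 10.4.3 to stop entry. Most of the literal *or* problem (710 of 900 pairs) is already caught, and the AHI 3.0 mismatch with item 2b's AHI limit is confined to the Study Summary.

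The point about the 12-month label stands as a qualifier, and an AHI-only endpoint beside a wider referral trigger is not in itself an error. But nothing says OSA means something different at entry, and the AHI-only reading still leaves two OSA definitions that classify the same PSG differently. The later checks state no OAI limit. Section 10.4.3 permits a site to stop such a child, but item 2b and central review do not require it, so sites could differ.

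**Conclusion.** The concern holds. A child with OAI above 1, AHI below 3 and no desaturation passes every written entry check, yet has a PSG that sections 2.1, 2.4.3 and 8.2 label OSA, while sections 6.2, 6.6 and 10.4.3 say OSA is excluded. This rests on applying the protocol's own 12-month label to the entry PSG, since no numeric entry definition is given, and on treating the index names as synonyms. The size in children is unknown because the documents give no joint distribution of OAI and AHI. The inconsistency at AHI exactly 3.0 does not depend on the connector.

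The co-primary analyses do not use these indices, and the SAP's AHI-only emergence endpoint can still be computed. What is affected is the description of the population and the statements about OSA at entry. It should be fixed, because following the rule as written can admit children whom the protocol says it excludes.

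**What to change.** Reconcile the Study Summary, sections 2.1, 2.4.3, 4.2 (item 2b), 5.2, 6.2, 6.6, 8.2, 9.1.2 and 10.4.3, and the SAP's study description and Aim 1 text, so that there is:
- one eligibility rule with one connector, one treatment of AHI 3.0, one set of index names and a clear scope for the desaturation clause;
- if OAI is part of the OSA exclusion, OAI named in the central-review rule;
- if *or* is intended, corrected exclusion statements and a corrected SAP premise about OSA at entry;
- a statement of whether the SAP's AHI-only definition is meant to differ from the either-index label.

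Then check that the eligibility logic, wherever it is implemented, matches. Which thresholds apply is for the investigators to decide. The cost is a wording amendment and that check; PSGs are already centrally scored, so no procedures are added.

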4.3. Exclusion Criteria

1. Previous tonsillectomy (whether partial, i.e., tonsillotomy, or complete tonsillectomy).
2. Recurrent tonsillitis that merits prompt AT per the American Academy of Otolaryngology-Head and Neck Surgery Clinical Practice Guidelines, i.e., ≥ 7

episodes/yr. in the past year; ≥ 5 episodes/year over the past 2 years or ≥ 3 episodes/yr. over the past 3 years².

3. Severe obesity (BMI z-score ≥ 3)
4. Severe chronic health conditions that might hamper participation or confound key variables under study. These conditions include, but are not limited to:
 - severe cardiopulmonary disorders (e.g. cystic fibrosis, congenital heart disease)
 - bleeding disorders
 - sickle cell disease
 - epilepsy requiring medication
 - other severe chronic health problems such as diabetes or narcolepsy.
 - mental retardation or assigned to a self-contained classroom for all academic subjects
 - known genetic, craniofacial, neurological, or psychiatric conditions likely to affect the airway, cognition, or behavior
 - psychiatric or behavioral disorders requiring or likely to require initiation of new medication, therapy, or other specific treatment during the 12-month trial period (other than ADHD).
5. Current use of psychotropic medication (other than medications for ADHD), hypnotics, antihypertensives or growth hormone. Note that children with ADHD will be included as it is possible that some cases of ADHD are secondary to MSDB
6. History of severe developmental disability or ABAS score < 60
7. Parent/guardian unable to accompany the child on the night of the PSG
8. Family planning to move out of the area within the year
9. Family does not speak English or Spanish well enough to complete the behavioral and performance measures.
10. Children in foster care.

